7.6 Double-Blind Treatment Assignment Unblinding

Prior to the Month 6 visit or early termination, the site will obtain the unblinded treatment assignment via the procedures described in the 7904 Manual of Procedures. At the conclusion of the double-blind phase or early termination, the blind will be broken immediately. Individuals on the active drug will exit the study, and those who were on placebo will be invited to join the open label phase (section 4.4).

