Tests that will be conducted during the blinded treatment phase include laboratory tests for safety, physical exams (including a neurological assessment), vital signs, and neuropsychological assessments. If unforeseen circumstances (i.e., unexpected personal reasons) prevent the patient from complying with the established visit schedule, the site can re-schedule the visit (within \pm 14 days of the expected visit date). The reason(s) for any visit or treatment delays will be documented in the CRF for the appropriate visit. All on-site visits (screening,

baseline, month 1, month 3, and month 6) must be completed by the participant, and any missed visits would warrant termination from the study. A summary of the neuropsychological results may be made available at study completion.

At the end of the double-blind phase (or early termination), the treatment code will be broken and the participant will be informed of their assigned treatment arm, using the process outlined in the 7904 Manual of Procedures. Participants who received the active compound will enter the follow-up phase of the study (section 4.5) and will be referred back to their treating physicians. Individuals who were in the placebo group will be invited to enter Phase B, a 6-month open-label extension trial (section 4.4). The inclusion of the open-label phase may increase the acceptability of the project by families and increase their participation in the primary, controlled trial. All participants that received everolimus during the blinded treatment phase will enter the follow-up phase of the trial and will be referred back to their treating physicians. A summary of patient's participation in the study will be provided, if needed.

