4.7 Early Termination

If the participant, legal guardian, or the study physician make the decision to have the participant exit the study early, a follow-up visit must be scheduled 28 days (+/- 14 days) after termination. At this visit, the study physician should review the patient's medical history, concomitant medications, and the DOTES. If the patient exited the trial due to an adverse event, this event should be reviewed and if it is still present the study team must follow-up with the patient/legal guardian for 56 days or until the event has subsided. At the completion of this follow-up visit, the participant may be unblinded and the results may be disclosed to the participant.

5. Recruitment Methods

Recruitment will leverage the observational study, The Natural History of Individuals with Autism and Germline Heterozygous PTEN mutations, and will occur at 3 sites: Cleveland Clinic, Stanford University, and Boston Children's Hospital, with Cleveland Clinic expected to recruit at least 50% of the sample based on extensive experience with PTEN patients at this site. Over the last 5 years, we have recruited and comprehensively evaluated 35+ patients with PTEN ASD only from referrals to Cleveland Clinic and word of mouth. We anticipate that the majority of these individuals would participate in the proposed study.

We will supplement our current recruitment efforts with several complementary strategies. First, [name] (Cleveland Clinic) has developed a registry of > 400 individuals with PTEN mutations that includes > 50 PTEN cases with ASD or evidence of developmental delay. To date, this registry has not been tapped, but it will be used to recruit individuals for the proposed study. [name] lab also regularly screens individuals at risk of PTEN mutations using an online risk calculator and extensive referral network – growing her registry. Second, the two additional sites, Stanford University and Boston Children's Hospital, also have experience with PTEN ASD patients and have an identified population that is interested in participating in this trial. Both of these sites will also leverage their relevant clinics to advertise and recruit for this study. Third, we have obtained support

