Dose adjustments will be permitted, based on safety findings and PK levels. The site PI will initiate any safety level related dose adjustments according to the protocol, in collaboration with the Medical Review Officer as appropriate. PK based dose adjustments will be initiated by the unblinded physician. All dose adjustments will be made using the 2.5mg tablets (i.e. increase by 2.5mg, decrease by 2.5mg, or maintain dose). If a dose adjustment is made for safety purposes, the unblinded physicians and Medical Review Officer should be made aware of any dose modifications as soon as possible.

Sites may substitute 5mg tablets (or 10mg tablets in open label) for 2.5mg tablets where necessary, as long as the single dose level increase or decrease is maintained. For example, an adjustment from 7.5mg to 10mg can be made by prescribing two 5mg tablets (or one 10mg tablet in open label) rather than one 5mg and two 2.5mg tablets. Following a dose adjustment, sites can mail the extra 5mg tablets to the participant in between visits to make up for the remaining days until the next site visit. One level dose increase would be increasing the dose by 2.5mg and a one level dose decrease would be decreasing the dose by 2.5mg as stated above.

Placebo Arm: Placebo dose adjustment procedures are defined in the unblinded dose adjustment protocol – accessible only to the unblinded physician(s) and the DMCC. The site team will be blinded with respect to treatment assignment at all times. [name], [name], and [name] will receive instructions regarding dose modifications for participants on placebo from the DMCC. When PK values become available for individuals in placebo arm, [name] or [name] will refer to the provided instructions and notify site Pl/coordinator of dose status (increase, decrease, or maintain) for individuals assigned to a dose adjustment.

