7.5 Randomization Procedure

Subjects will be randomized 1:1 to everolimus or placebo after meeting all eligibility criteria. A designated member of the research team will communicate to the participant that randomization has occurred and sufficient study drug will be dispensed to cover the interval until the next study visit. This is a double-blind study. The study design allows patient unblinding during the double-blind phase only in very precise circumstances (section 7.6.1).

Randomization data are to be kept strictly confidential until the time of unblinding at discontinuation or at the time of final analysis. These data will not be accessible to anyone involved in the conduct of the study with the exception of the unblinded physicians, the Medical Monitor, the Data Safety and Monitoring Committee (DSMC), and the Data Management Coordinating Center (DMCC). The DSMC will review safety data as outlined in section 15. The identity of treatment arms will be concealed by the use of study drugs (everolimus and matching placebo) that are identical in packaging, labeling, schedule of administration and in appearance.

Prior to Baseline (Visit 2), the investigator or his/her designee will log onto the data system to verify that the patient fulfills all eligibility criteria and randomize the patient to a treatment arm. The system will assign a randomization arm, as described in the 7904 Manual of Procedures. The pharmacy will be responsible for dispensing the active drug or placebo based on the procedures outlined in the 7904 Pharmacy Manual of Procedures. The randomization will be stratified by age. Age will be stratified by two levels. Level 1 will be participants aged 5-21 years old, and level 2 will be 22-45 year olds. Permuted block sizes of two and four will be used. At the conclusion of the 6-month double-blind phase, the blind will be broken immediately. Individuals on the active drug will exit the study, and those who were on placebo will be invited to join the open label phase.

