7.16.8 Blood Sample for Everolimus (Everolimus Levels)

A maximum volume of 3 ml of blood will be drawn for a trough everolimus level. Blood draws will be timed to occur at 24 \pm 4 hours after ingestion of the drug. Everolimus levels will be measured at ARUP Laboratories associated with LabConnect in Salt Lake City, UT. For families that do not live close to the study site, there are

two options for remote blood collection. A kit for remote collection of blood samples can be sent to the participant and returned per the shipping instruction by express mail, or a designated and trained remote health care provider can collect a PK sample and ship it per the shipping instruction by express mail. A central unblinded investigator will be responsible for dose adjustment in both the treatment and placebo arms. If the everolimus level falls outside the range of 5-15 ng/ml, the local research team and PI will be notified that a dose adjustment is needed, the dose adjustment will be implemented by the local investigator per protocol and unblinded investigator direction, and the blood level will be redrawn two weeks (+/- one week) later. The site team is blinded with respect to treatment assignment at all times. This process will be repeated until the everolimus level falls within the target range. Dose adjustments will be randomly pre-assigned to occur in the placebo arm of this trial. The DMCC will assign dose adjustments to placebo randomization codes and share this information with the unblinded physician who will facilitate a dose adjustment at the appropriate time-point for these placebo participants.

A pre-dose trough blood sample will be collected immediately prior to dosing at month 1 (visit 3). This sample should be collected prior to the patient's next dose of study drug \sim 24 \pm 4 hours after the last dose. The central unblinded investigator will be responsible for dose adjustment, using the 2.5mg tablets, to achieve the target everolimus concentration range of 5-15 ng/ml. Sites may substitute 5mg or 10mg tablets as described in Section 6.2.

Additional pre-dose trough blood samples will be taken if a dose adjustment occurs due to toxicity or due to concomitant medication dose adjustment (See Section 7.6.3). Should clinically significant changes in the patient's height and/or weight occur at any time point during the study, the principal investigator may choose to have additional pre-dose trough blood samples taken.

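### Section 7.6 gives the site the treatment code before the Month 6 visit or early termination, against 7.5 and 4.3, and no text requires assessments to come first

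*Combined protocol and SAP*

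**What the plan says.** Section 7.6 opens: "Prior to the Month 6 visit or early termination, the site will obtain the unblinded treatment assignment via the procedures described" in the Manual of Procedures. Its next sentence reads: "At the conclusion of the double-blind phase or early termination, the blind will be broken immediately".

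Other sections bear on who may know the assignment, and when:

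- Section 4.3: "At the end of the double-blind phase (or early termination), the treatment code will be broken and the participant will be informed".
- Section 7.5: "Randomization data are to be kept strictly confidential until the time of unblinding at discontinuation or at the time of final analysis". On access: "These data will not be accessible to anyone involved in the conduct of the study with the exception of the unblinded physicians", followed by the Medical Monitor, the DSMC and the DMCC. The same section permits unblinding during the double-blind phase only under the emergency provision, 7.6.1.
- Dose-adjustment text in Section 6 (placebo-arm paragraph): "The site team will be blinded with respect to treatment assignment at all times". Section 7.16.8 repeats it: "The site team is blinded with respect to treatment assignment at all times".
- Section 4.7, for early termination, refers to the visit 28 days later: "At the completion of this follow-up visit, the participant may be unblinded and the results may be disclosed to the participant".
- Section 4.4 uses the Month 6 scores both as blinded-phase data and as open-label baseline, and expects staff to be ready to dispense open-label drug at that visit.
- Table 13A marks participant unblinding in the Month 6 column and gives no order within the visit.
- Section 7.9.1 states that raters are blinded for CGI-S, CGI-I and ADOS-2. Section 7.10 adds blinded reading of skin photographs where feasible. The tests in the neurocognitive composite have no specific statement of this kind.

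**The concern.** Month 6 (Visit 8) belongs to the double-blind phase. If the site holds the code before that visit, the people who give the tests may know the arm when they give them. Section 17 singles out the 6-month group difference as of particular interest. Section 17.1 makes the composite a Phase III candidate if it reaches a one-sided nominal p below .05. The value of that comparison depends on the testing having been blinded.

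The same sentence covers early termination. Staff who know the arm before a patient's participation ends could be influenced when they record why treatment stopped, and the primary endpoint is drop-out due to side effects.

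**Working it through.** **1. Timing of the code for Month 6.**

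| Place | When | Who |
|---|---|---|
| 7.6, sentence 1 | before the Month 6 visit | the site, no role named |
| 7.6, sentence 2 | at the conclusion of the phase | not stated |
| 4.3 | at the end of the phase | participant informed |
| 7.5 | at the conclusion of the phase; earlier only under 7.6.1 | access list has no site investigator or tester |
| Section 6 dose text, 7.16.8 | site team blinded at all times | site team |

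Routine retrieval before Visit 8 is not an emergency under 7.6.1, so sentence 1 contradicts 7.5 directly. The at-all-times statements are weaker evidence. They sit in dose-adjustment text and, read literally, would also rule out the planned end-of-phase unblinding.

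**2. Timing for early termination.** Sentence 1 of 7.6 puts retrieval before termination. Sentence 2 and 4.3 put the code break at termination. Section 7.5 allows unblinding at discontinuation. Section 4.7 says the participant may be unblinded after the 28-day follow-up visit. Section 7.7.6 schedules the End of Treatment assessments as soon as possible after the drug is stopped and does not place them before or after the code break. These rules do not agree.

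**3. Is there an ordering rule?** Section 4.4 implies that Month 6 testing comes first, because it calls the scores blinded-phase data. Section 4.7 sets an order for telling the participant after early termination. Neither says that assessments must be finished before the site receives the code.

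**4. What is exposed at Month 6.** From Tables 11 and 13A, seven direct tests have no stated blinded rater: SB-5 or Mullen, CPT, Wechsler PSI, WRAML-2, PPVT-4, EVT-2 and Purdue Pegboard. The VABS-III is mixed: it is listed as caregiver report, but 7.9.4 describes a tester interview. The other six forms (SRS-2, RBS-R, DCDQ, BRIEF, CBCL, Short Sensory Profile) are completed by the caregiver or the patient. Sentence 1 does not give the code to families, so these six are exposed only if the arm is disclosed before they are filled in.

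**5. Numbers of patients.** Applying the roughly 10% dropout in 17.1 to 40 randomized: 0.10 × 40 = 4 stop early, 36 reach Month 6, 18 per arm. Section 17.1 also speaks of enrolling 44 to have 40 complete, which would be 20 per arm.

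**6. Illustration of consequence.** The shift b is assumed; no document supplies it. Take no drug effect, SD 1, 18 per arm, one-sided 5%, 34 df. The false-positive rate is P(noncentral t > 1.691) with noncentrality b/SE.

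- Endpoint comparison: SE = √(2/18) = 0.333.
- Linear slope over 0, 3 and 6 months, compound symmetry, weights −1, 0, +1, shift at Month 6 only: SE = √(2(1−r) × 2/18). This is √(1.4 × 2/18) = 0.394 at r = .30, the lowest correlation assumed in 17.1, and √(0.6 × 2/18) = 0.258 at r = .70, an assumed higher value.

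| Average shift b (SD) | Endpoint | Slope, r = .30 | Slope, r = .70 |
|---|---|---|---|
| 0 | 5% | 5% | 5% |
| 0.1 | 9% | 8% | 10% |
| 0.2 | 15% | 13% | 19% |
| 0.3 | 22% | 18% | 31% |

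With 20 per arm the endpoint SE is √(2/20) = 0.316, so the rates would be slightly higher. If only one third of assessments were shifted by 0.3 SD, the average would be 1/3 × 0.3 = 0.1 SD.

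**The case against.** The best defence is a two-step reading: a designated person retrieves the code beforehand so that open-label drug is ready under 4.4, and the blind is broken only at the end. Sections 7.6 and 4.3 both leave the process to the Manual of Procedures, which is not among the documents and may restrict who sees the code. This stands as a reason not to assert that anyone is unblinded early. It does not cure the text: the protocol itself sets the time and the recipient, and it names the whole site.

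The access list in 7.5 is also not exhaustive. The pharmacy dispenses active drug or placebo, and an unblinded research nurse exists, yet neither is listed. The absence of a site role is therefore weak evidence alone. The restriction to 7.6.1 is the firmer conflict.

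The double-blind label and the at-all-times statements cover testers in general terms, and 7.9.3 calls the composite measures objective. Both limit the worry. Neither sets an order within the Month 6 visit, and standardized administration limits tester influence without removing it.

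A reader might infer that the primary endpoint is compromised. The documents do not support that. Month 6 completers cannot change it, about 4 early terminators could be involved, and 7.7.6 forbids recording a stop caused by an adverse event or laboratory abnormality as withdrawn consent. No rate of misrecorded reasons can be derived.

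**Conclusion.** Wrong as written. The opening sentence of 7.6 conflicts with 7.5, 4.3 and its own next sentence, and nothing in the protocol puts the assessments before the site's receipt of the code. The early-termination timing in 4.3, 4.7 and 7.6 is also unreconciled. These conclusions rest on the text alone and are firm.

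The consequence is less certain. At stake is the blinding of seven direct tests, and of the VABS-III where it is done by interview, at the 6-month efficacy comparison, in about 36 patients. A reader might infer that Month 6 testers are in fact unblinded, that families learn the arm before completing their forms, or that the efficacy test has a known inflated error rate. None of these is shown. The size of any bias cannot be estimated from the documents. The tabulated rates show only what an assumed shift would do, and the slope figures depend on r as well. Any effect on the primary endpoint is confined to early terminators and is small. The point should be fixed because the correction is cheap and protects the comparison that informs Phase III.

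**What to change.** Reword 7.6 so that:

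- any advance retrieval for open-label supply is limited to the pharmacy or the existing unblinded nurse or coordinator;
- the assignment goes to other site staff and the family only after the Month 6 or early-termination tests, ratings and forms are completed or recorded as not done (refused, unable, or remote visit), and any discontinuation reason is recorded;
- testers of the composite are stated to stay blinded until release.

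The not-done option is needed because 7.7.6 foresees patients who refuse a final visit, 7.9 foresees tasks that cannot be completed, and 4.3 allows remote visits. Without it, some patients could never be unblinded. Central laboratory results and later events stay under existing follow-up and need not delay release.

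Reconcile the early-termination unblinding time across 4.3, 4.7 and 7.6, and align the Manual of Procedures and Table 13A. Leave emergency unblinding in 7.6.1 unchanged.

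Cost: a written amendment with the reviews listed in Section 18 (central IRB, Cleveland Clinic IRB, NIH and Novartis, as applicable) in a trial already open to enrollment, plus a release condition in the database. Open-label drug would be dispensed at the end of the visit or within the return window that 4.4 already allows.

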7.6.1 Emergency Unblinding Treatment Assignment

In general, circumstances that might lead to emergency unblinding are rare. Most often, study drug discontinuation and knowledge of the possible treatment assignments are sufficient to treat a study patient who presents with an emergency condition. One unusual circumstance in which unblinding might be necessary is when a patient requires emergency surgery and the anesthesiologist needs to know all medications that the patient has been exposed to in order to make proper decisions about treatment and support during the surgery.

Emergency unblinding should only be done when necessary in order to treat the patient. Emergency code breaks are performed using the database, as described in the 7904 Manual of Procedures.

It is the investigator's responsibility to ensure that there is a procedure in place for emergency unblinding. The investigator will inform the patient how to contact his/her backup in cases of emergency when he/she is unavailable.

Study drug must be discontinued after emergency unblinding. The investigator is not allowed to place emergency unblinded patients into open-label everolimus therapy.

7.7 Treating the Patient

7.7.1 Study Drug Administration

Everolimus or placebo will be dispensed by the study center personnel on an outpatient basis. Patients will be provided with study drug at Visit 2 (Baseline), and each subsequent on-site visit for self-administration at home.

The first dose of everolimus or placebo must be taken within 7 days of Visit 2 (Baseline). Patients will be instructed to take everolimus or placebo by mouth regularly, with the dose being taken at the same time in the morning every day. Everolimus or placebo tablets should be swallowed whole with a glass of water. The tablets should not be chewed or crushed. Any dietary habits around the time of everolimus or matching placebo intake should be as consistent as possible throughout the study. The extent of absorption of everolimus through topical exposure is not known. Therefore, patients/caregivers are advised to avoid contact with the everolimus or placebo tablets and should wear gloves and should wash their hands thoroughly before and after administration. If vomiting occurs, no attempt should be made to replace the vomited dose. Patients should be instructed that if they miss a dose one day, they must not take any extra dose the next day.

Patients should be requested to bring their unused study drug, including the empty blister packs, to the clinic at each visit.

Patients will receive treatment with study drug for 6 months or until the occurrence of unacceptable toxicity or the investigator or patient decides that continuation is not in the best interest of the patient. Interruption for toxicity should follow the instructions in Table 3.

7.7.2 Treatment Compliance

Compliance should be verified by the investigator's staff through counting the number of tablets consumed between visits. Compliance will be assessed by the investigator or his/her designee at each visit using pill counts and review of the drug diary. The site must maintain an overall drug accountability log for the study, as well as individual accountability records for each patient. The dose, amount dispensed, amount taken, and amount remaining unused must be recorded in the source document. The patient will return all unused study drug at each dispensing visit, except Visit 2/Baseline, and at the End of Study visit.

- Patients will be requested to bring their unused medication including empty packaging to the clinic at each visit.
- All doses taken by the patient and all dose changes during the study must be recorded on the Dosage Administration Record CRF and the Dose Adjustment Log CRF, respectively.
- The investigator or his/her designee must keep documentation (overall drug accountability log for the study as well as individual study drug accountability records for each patient) of tablets administered, tablets used, dose changes, dates dispensed and intervals between visits.

